7.2 STUDY SCHEDULE

The information contained in this protocol and all other information relevant to this study are confidential and proprietary information of Strata Oncology Inc., except as may be required by federal, state or local laws or regulation, and may not be disclosed to others without prior written permission of Strata.

Page 31 of 56

7.2.1 SCHEDULE OF ACTIVITIES

The schedules of activities (SOA) for both the tdMeta and μMeta cohorts are detailed in **Table C** and **Table D**. StrataPATH is designed to mimic real-world practice and will have a limited number of study-specific visits (**Section 7.1**). The visit schedules are comprised of a combination of study-specific visits and standard of care (SOC) visits. Participants will be followed for up to 3 years from the time of consent.

SOC procedures listed in the SOA typically occur during standard clinical visits and are to be documented within the EDC system at the timepoints outlined in the SOA.

The information contained in this protocol and all other information relevant to this study are confidential and proprietary information of Strata Oncology Inc., except as may be required by federal, state or local laws or regulation, and may not be disclosed to others without prior written permission of Strata.

Page 32 of 56

Table C: StrataPATH Schedule of Activities – tdMeta Cohorts

SCHEDULE OF ACTIVITIES STR-004-001: StrataPATH tdMeta Cohorts	STUDY VISITS (participation up to 3 years)			
	Screening	Baseline	On Treatment	Post-Treatment ^g
Study Procedures				
Review and Sign Informed Consent Form	X			
Eligibility Criteria Review (Main and Cohort-Specific)	X	X		
Biomarker Confirmation	X			
CT Scan or MRI of Abdomen, Chest, and Pelvic Area		X ^a	X ^{b,c}	
RECIST 1.1 (or iRECIST) Assessment		X	X ^{b,c}	
Blood Draw: Whole Blood		X	X ^{b,c}	
FFPE Tissue Collection	X ^d			
Study Drug Administration		X ⁱ	X ⁱ	
Study Drug Accountability		X	X	X ^h
Study Drug Discontinuation				X ^h
Standard of Care (SOC) Procedures^e				
Documentation of Biomarker Results	X ^e			
Demographics	X ^e			
Medical History	X ^{e,f}		X ^e	X ^e
Cancer Diagnosis	X ^e			
Prior and Concomitant Medications	X ^{e,f}		X ^e	X ^e
Physical Exam (Complete or Abbreviated)	X ^e		X ^e	X ^e
ECOG Performance Status	X ^e	X ^e	X ^e	X ^e
Height, Weight, Vital Signs	X ^e		X ^e	X ^e
Electrocardiogram (EKG)	X ^j		X ^e	X ^e
Echocardiogram (Echo)	X ^j			
Hematology	X ^e		X ^e	X ^e
Serum Chemistry	X ^e		X ^e	X ^e
Urine Pregnancy Test, Serum Pregnancy Test ^k	X ^e	X ^e	X ^e	
Safety Evaluation				
Adverse Events/Serious Adverse Events		X	X	X

^aIf a scan was performed within 28 days of the baseline visit, these results should be submitted to the study.

^bCollect every 8 weeks (± 2 weeks) during year 1 on treatment. After year 1 of treatment, collect every 12 weeks (± 2 weeks). Collect upon disease progression.

^cConfirmation of progression (e.g., confirmatory scan 4 weeks after initial progression assessment).

^dOnly required if historical comprehensive genomic or Strata RNA profiling results are not available or otherwise indicated within the cohort-specific criteria. Site should collect and submit a leftover tumor tissue specimen to the Strata Lab for confirmatory testing with a central next generation sequencing test.

^eThe specified SOC procedures should be conducted only if they are necessary for clinical care and should not be done for research purposes only. If any of these SOC activities are conducted at a regular clinic visit, the data obtained must be entered in the EDC for the study.

^fEnter information from medical records obtained up to 30 days prior to the screening visit.

^gEvery 3 months for up to 3 years from the date of consent or until death, whichever comes first.

^hStudy drug will be discontinued upon progression or per physician discretion. Study drug discontinuation and accountability activities will only be performed once during post-treatment.

ⁱThe frequency of study drug dispensing and administration will be determined by the biomarker/study drug cohort in which the patient is enrolled.

^jIf not SOC and historical data not available, can be research activity.

^kOnly if urine test is positive or inconclusive; serum test can be research activity.

The information contained in this protocol and all other information relevant to this study are confidential and proprietary information of Strata Oncology Inc., except as may be required by federal, state or local laws or regulation, and may not be disclosed to others without prior written permission of Strata.

Page 33 of 56

Table D: StrataPATH Schedule of Activities – μMeta Cohorts

SCHEDULE OF ACTIVITIES μMeta Cohorts STR-004-001 - StrataPATH	STUDY VISITS (participation up to 3 years)			
	Screening	Baseline	On Treatment	Post-Treatment ^e
Study Procedures				
Review and Sign Informed Consent Form	X			
Eligibility Criteria Review (Main and Cohort-Specific)	X	X		
Biomarker Confirmation	X			
Blood Draw: Whole Blood		X	X ^b	
FFPE Tissue Collection	X ^a			
Study Drug Administration		X ^g	X ^g	
Study Drug Accountability		X	X	X ^f
Study Drug Discontinuation				X ^f
Standard of Care (SOC) Procedures				
Documentation of Biomarker Results	X ^c			
Demographics	X ^c			
Medical History	X ^{c,d}		X ^c	X ^c
Cancer Diagnosis	X ^c			
Prior and Concomitant Medications	X ^{c,d}		X ^c	X ^c
Physical Exam (Complete or Abbreviated)	X ^c		X ^c	X ^c
ECOG Performance Status	X ^c	X ^c	X ^c	X ^c
Height, Weight, Vital Signs	X ^c		X ^c	X ^c
Electrocardiogram (EKG)	X ^h		X ^c	X ^c
Echocardiogram (Echo)	X ^h			
Hematology	X ^c		X ^c	X ^c
Serum Chemistry	X ^c		X ^c	X ^c
Urine Pregnancy Test, Serum Pregnancy Test ⁱ	X ^c	X ^c	X ^c	
Safety Evaluation				
		X	X	X

^aOnly required if historical comprehensive genomic or Strata RNA profiling results are not available or otherwise indicated within the cohort-specific criteria. Site should collect and submit a leftover tumor tissue specimen to the Strata Lab for confirmatory testing with a central next generation sequencing test.

^bCollected every 8 weeks (± 2 weeks) during year 1 on treatment. Collect every 12 weeks (± 2 weeks) after year 1 on treatment. Collect upon disease progression.

^cThe specified SOC procedures should be conducted only if they are necessary for clinical care and should not be done for research purposes only. If any of these SOC activities are conducted at a regular clinic visit, the data obtained must be entered in the EDC for the study.

^dEnter information from medical records obtained up to 30 days prior to the screening visit.

^eEvery 3 months for up to 3 years from the date of consent or until death, whichever comes first.

^fStudy drug will be discontinued upon progression or per physician discretion. Study drug discontinuation and accountability activities will only be performed once during the post-treatment phase.

^gThe frequency of study drug dispensing and administration will be determined by the biomarker/study drug cohort in which the patient is enrolled.

^hIf not SOC and historical data not available, can be research activity.

ⁱOnly if urine test is positive or inconclusive; serum test can be research activity.

The information contained in this protocol and all other information relevant to this study are confidential and proprietary information of Strata Oncology Inc., except as may be required by federal, state or local laws or regulation, and may not be disclosed to others without prior written permission of Strata.

Page 34 of 56

7.2.2 tdMETA COHORTS

7.2.2.1 SCREENING

- Obtain informed consent of potential participant verified by signature on written informed consent form
- Review medical history, including biomarker status and cancer diagnosis, to determine eligibility based on inclusion/exclusion criteria (**Sections 5.1-5.2**)
- Enter data from any standard of care procedures in the EDC
- Submit biomarker confirmation form
- If no historical Strata CGP or RNA profiling test results are available, submit a left-over FFPE tumor specimen for confirmation by a central lab

7.2.2.2 BASELINE

- Verify eligibility per inclusion/exclusion criteria
- Review of medications
- Negative pregnancy test (urine or serum)

- Obtain two 10 mL tubes of whole blood
 - Complete research blood collection form
- Conduct CT scan or MRI of abdomen, chest, and pelvic area
 - If a scan was conducted within 28 days of the baseline visit, these results should be submitted; an additional scan is not required for the baseline visit.
- Complete RECIST 1.1 (or iRECIST) assessment
- Dispense study drug and review dosing instructions
- Administer study drug and/or review administration instructions with participant
- Perform drug accountability
- Enter data from any standard of care procedures in the EDC, including ECOG status
- Document any AEs or SAEs

7.2.2.3 ON TREATMENT

- Review of medications
- Negative pregnancy test (urine or serum)
- Obtain two 10 mL tubes of whole blood every 8 weeks during the first year of treatment and every 12 weeks thereafter and once upon disease progression

The information contained in this protocol and all other information relevant to this study are confidential and proprietary information of Strata Oncology Inc., except as may be required by federal, state or local laws or regulation, and may not be disclosed to others without prior written permission of Strata.

Page 35 of 56

- Complete research blood collection form
- Conduct CT scan or MRI of abdomen, chest, and pelvic area every 8 weeks during the first year of treatment and every 12 weeks thereafter
 - At progression, perform a confirmatory CT scan or MRI (e.g., 4 weeks after initial progression assessment)
- Complete RECIST 1.1 (or iRECIST) assessment every 8 weeks during the first year of treatment and every 12 weeks thereafter
 - At progression, perform RECIST 1.1 (or iRECIST) assessment (e.g., 4 weeks after initial progression assessment)
- Dispense study drug
- Administer study drug and/or review administration instructions with participant
- Perform drug accountability
- Enter data from any standard of care procedures in the EDC, including ECOG status
- Document any AEs or SAEs

7.2.2.4 POST-TREATMENT

Study drug will be discontinued upon disease progression or based on physician's discretion as described in **Section 5.5**. Site staff should collect unused study drug and any empty packaging and perform drug accountability upon study drug discontinuation. Participants that discontinue drug will remain on study for 3 years from the date of informed consent for follow-up data entry purposes only. No additional study specific procedures will occur following discontinuation. Participants will continue to see their physician for SOC clinic visits. Site staff will be responsible for collecting and entering the information below in EDC from the participants SOC clinic visits every 3 months.

- Medical history (specifically, disease recurrence and/or survival status)
- Concomitant medications (specifically, anticancer therapies)
- Standard of care procedures, including ECOG status

7.2.3 μMETA COHORTS

Note that μMeta cohorts will not have CT/MRI scans or RECIST 1.1 (or iRECIST) assessments performed.

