3 OBJECTIVES AND ENDPOINTS

3.1 OBJECTIVES AND ENDPOINTS

All endpoints will be assessed independently for each biomarker-defined cohort. **Tables A and B** list the objectives and endpoints for this study. Cohorts are stratified based on disease

The information contained in this protocol and all other information relevant to this study are confidential and proprietary information of Strata Oncology Inc., except as may be required by federal, state or local laws or regulation, and may not be disclosed to others without prior written permission of Strata.

Page 19 of 56

severity: (1) traditionally defined metastatic/advanced (tdMeta), and (2) micro-metastatic (μ Meta).

Table A: StrataPATH Objectives and Endpoints for tdMeta Cohorts

tdMeta Cohorts	
OBJECTIVES	ENDPOINTS
Primary	
Assess the clinical activity of anti-cancer therapies in participants with pre-specified biomarker profiles.	ORR – Overall Response Rate is defined as the percentage of participants with a best overall response of CR or PR based on Response Evaluation Criteria in Solid Tumors (RECIST) 1.1, as assessed by the investigator.
Secondary	
Assess the duration of response in anti-cancer therapies in participants with pre-specified biomarker profiles.	
 DoR – Duration of response is defined as the time from first documentation of disease response (CR or PR) until first documentation of progressive disease. TTD – Time to treatment discontinuation is defined as length of time from the date the participant initiates the systemic treatment to the date the participant discontinues treatment TTnT – Time to next treatment is defined as the length of time from the date the participant initiates study treatment to the date the participant initiates their next systemic treatment or death.
Evaluate ctDNA response rate at timepoints for participants who received anti-cancer therapies with pre-specified biomarker profiles.	ctDNA response – Proportion of participants with a <50% ratio of mean VAF will be defined as ctDNA responders. Molecular response is calculated as a ratio of mean VAF on-treatment at different timepoints compared to their baseline VAF.
Evaluate overall survival (OS) for participants who received an anticancer therapy with pre-specified biomarker profiles.	OS – Time from initiation of treatment until death from any cause.
Monitor and characterize the overall safety in the biomarker cohorts	The incidence of serious adverse events (SAEs).
Exploratory	

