Tumor assessments to support ORR efficacy assessment will be completed as outlined in the Study Schedule of Activities (**Section 7.2**) and recorded in the study database. Study staff will also record information in the study EDC (either manually or through an integrated mechanism) which occur as part of standard of care visits. Standard of care details such as demographics, clinical characteristics, and concomitant medications will be recorded within the study database. Upon identification of any efficacy signal, additional real-world data collection may be requested (i.e., additional medical history and imaging) to support additional analysis and cohort expansion studies. Following completion of or discontinuation from drug, all active study participants will be followed for survival for 3 years from the date of consent.

This study will require reporting of Common Terminology Criteria for Adverse Events (CTCAE) grade 3 and 4 AEs that are possibly, probably, or definitely related to the study treatment. All SAEs, regardless of grade, relatedness to study drug, or expectedness, must be reported, including deaths.

Drug/biomarker cohorts may be added, changed, or discontinued over time. This study may enroll up to 700 participants.

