5.8 LOST TO FOLLOW-UP

A participant will be considered lost to follow-up if they fail to return for 2 consecutively scheduled visits and are unable or unwilling to be contacted by the study site staff.

The information contained in this protocol and all other information relevant to this study are confidential and proprietary information of Strata Oncology Inc., except as may be required by federal, state or local laws or regulation, and may not be disclosed to others without prior written permission of Strata.

Page 28 of 56

The following actions must be taken if a participant fails to return to the clinic for a required study visit:

- The site will attempt to contact the participant and reschedule the missed visit within a week and counsel the participant on the importance of maintaining the assigned visit schedule and ascertain if the participant wishes to and/or should continue in the study.
- Before a participant is deemed lost to follow-up, the investigator or designee will make every effort to regain contact with the participant (where possible, 3 telephone calls and, if necessary, a certified letter to the participant's last known mailing address or local equivalent methods). These contact attempts should be documented in the participant's medical record or study file.
- Should the participant continue to be unreachable, they will be considered to have withdrawn from the study with a primary reason of lost to follow-up.

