7.2.3.4 POST-TREATMENT

Study drug will be discontinued upon disease progression or based on physician's discretion as described in **Section 5.5**. Site staff should collect unused study drug and any empty packaging and perform drug accountability upon study drug discontinuation. Participants that discontinue drug will remain on study for 3 years from the date of informed consent for follow-up data entry purposes only. No additional study specific procedures will occur following discontinuation. Participants will continue to see their physician for SOC clinic visits. Site staff will be responsible

The information contained in this protocol and all other information relevant to this study are confidential and proprietary information of Strata Oncology Inc., except as may be required by federal, state or local laws or regulation, and may not be disclosed to others without prior written permission of Strata.

Page 37 of 56

for collecting and entering the information below in EDC from the participants SOC clinic visits every 3 months.

- Medical history (specifically, disease recurrence and/or survival status)
- Concomitant medications (specifically, anticancer therapies)
- Standard of care procedures, including ECOG status

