9.3.2 EFFICACY ANALYSES

Efficacy analyses for ORR and DoR are based on the responses from Investigator-recorded measurements and assessments for target, nontarget, and new lesions according to RECIST 1.1.²¹

- ORR is defined as the percentage of participants with a best overall response of complete response (CR) or partial response (PR).
- DoR is defined as the time from first documentation of disease response (CR or PR) until first documentation of progressive disease.

Efficacy analyses for ctDNA response rate will be based on the proportion of participants considered responders compared to non-responder participants. Responders are defined as any participant with <50% ratio of mean VAF.

ORR and ctDNA response rate will be estimated by the proportion of participants with objective response and ctDNA response respectively and their 95% confidence intervals will be estimated using the exact binomial method. Other time-to-event efficacy analyses including TTD, TTNT, DFS and OS will be summarized using the Kaplan-Meier method with the appropriate time-defined cut-offs.

Additional supportive analyses of efficacy endpoints may be conducted using iRECIST.²²

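### After study drug stops, clinic visits are the only routine source named for survival status and no route finds deaths once contact fails, so overall survival may be biased upward.

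*Protocol*

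**What the plan says.** Protocol section 3.1 (Tables A and B) makes overall survival a secondary endpoint in both kinds of cohort, defined as "Time from initiation of treatment until death from any cause". Section 9.3.2 says that it "will be summarized using the Kaplan-Meier method with the appropriate time-defined cut-offs".

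Section 4.1 states that, after drug ends, "all active study participants will be followed for survival for 3 years from the date of consent". Section 4.3 counts a treated participant as having completed the study after that 3-year survival follow-up or at death.

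The working instructions are in 7.2.2.4 (tdMeta) and 7.2.3.4 (μMeta). Both say of the period after drug stops: "No additional study specific procedures will occur following discontinuation". Under 7.2.2.4 site staff are responsible for "collecting and entering the information below in EDC from the participants SOC clinic visits every 3 months", and 7.2.3.4 repeats this. Survival status is one of the medical history items collected this way.

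Section 5.8 defines loss to follow-up as two consecutive missed scheduled visits without contact. Its contact steps open with "The following actions must be taken if a participant fails to return to the clinic for a required study visit". They comprise three calls where possible and a certified letter if needed. If these fail, "they will be considered to have withdrawn from the study with a primary reason of lost to follow-up".

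**The concern.** Kaplan-Meier assumes that a person censored at a given time has the same future risk as those still under observation. Attendance-based follow-up strains that assumption. Section 2.3 describes the tdMeta participants as having few or no treatment options left, and drug is stopped on progression. Those who then stop attending, for example because they enter hospice or move to another hospital, are plausibly those closest to death. If such a death is never learned of, the person is censored shortly before dying and the survival curve sits too high.

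The loss cannot be repaired at analysis. A statistical analysis plan can set a censoring rule, but it cannot supply death dates that were never collected. There is no control arm in which the bias might cancel. Death is also an event in TTnT (tdMeta) and DFS (μMeta), so the same gap touches those endpoints. Section 3.2.1 treats overall survival as the reference for TTD and TTnT.

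**Working it through.** The protocol gives no expected survival, loss-to-follow-up rate or share of deaths missed, so it has no figure to reproduce. The check has two parts.

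**1. Can a death outside the clinic reach the database?**

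- *Routine source:* standard-of-care visits (7.2.2.4, 7.2.3.4). A person who no longer attends generates no entry.
- *Contact steps in 5.8:* the trigger is a missed required visit, and two consecutive visits must be missed. At 3-monthly intervals that is about 2 × 3 = 6 months. The calls and letter may bring a death to light. If they do not, the participant is classed as withdrawn and no further search is described.
- *Death reporting in 8.2.8:* this is a duty to report deaths during the study. It names no means of learning of one.
- *Survival follow-up in 4.1:* it covers active participants, so the withdrawn label plausibly ends it.

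No section names a scheduled survival call, contact with relatives or a death-record check.

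**2. How large could the bias be?**

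Assumed inputs, none of them from the protocol: exponential survival with true median *m* of 6, 12 or 18 months, and a share *q* of deaths missed (5% to 30%). Taken from the protocol: 3-monthly contacts and a 36-month horizon (approximated as running from treatment start).

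If a share *q* of deaths is unseen and those people are censored near death, the visible hazard is about (1 − *q*) times the true one. Then:

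- apparent median ≈ *m* / (1 − *q*)
- apparent 12-month survival ≈ 0.5^(12(1 − *q*)/*m*)

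For *m* = 12 and *q* = 10%: 12 / 0.9 = 13.3 months, and 0.5^0.9 = 53.6%.

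A simulation of 400,000 survival times per scenario, with each missed death censored at the preceding 3-monthly contact, gives for *m* = 12:

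| Deaths missed | Median, formula | Median, simulated | 12-month OS, formula | 12-month OS, simulated |
|---|---|---|---|---|
| 0% | 12.0 | 12.0 | 50.0% | 50.0% |
| 5% | 12.6 | 12.6 | 51.8% | 51.6% |
| 10% | 13.3 | 13.2 | 53.6% | 53.3% |
| 20% | 15.0 | 14.7 | 57.4% | 56.9% |
| 30% | 17.1 | 16.7 | 61.6% | 60.8% |

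The simulated values are slightly lower because censoring at the last contact removes people from the risk set a little early.

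Over the same range of *q*, a true median of 6 months becomes 6.3 to 8.2, and 18 months becomes 18.9 to 25.3.

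If missed deaths were instead carried as alive to month 36, 12-month survival for *m* = 12 would be 1 − 0.5(1 − *q*), that is 52.5%, 55.0%, 60.0% and 65.0%. The simulated medians are then 13.0, 14.0, 17.0 and 21.6 months.

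**The case against.** A reader might infer that clinic visits are the only source of survival data, that deaths are missed, and that overall survival is overstated in every cohort. The protocol does not support that reading.

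- Table C lists the post-treatment period among the study visits, every 3 months, so the 5.8 calls and letter plausibly apply after drug stops and would find some deaths.
- Section 8.2.8 requires deaths during the study to be reported, and participants who stop drug stay on study for 3 years.
- Section 8.1 already draws data from electronic health records. The operations manual, which is not shown, may say more about tracing.
- Section 6.4 asks for remaining procedures to be completed after dosing stops. Section 7.3.1 continues tumor assessments in those who stop for reasons other than progression, so the statement that no study procedures follow discontinuation is not the whole text.
- The mechanism concerns advanced disease. It carries much less weight in the μMeta cohorts, whose participants have no overt metastases.
- No rate of missed deaths is given, so every figure above rests on an assumed share. At 5% the effect is small.
- Overall survival is secondary with no hypothesis test. The stage and success rules in 9.1 use response only, and section 9 specifies no analysis of TTD or TTnT against overall survival.

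All of this stands, and it reduces the point to a risk of unknown size. It does not close the gap: none of these sections provides a way to learn of a death after contact fails, or keeps the unreachable participant in survival follow-up.

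**Conclusion.** The point holds in limited form. The protocol commits to 3-year survival follow-up, names only clinic visits as the routine source after drug stops, and ends at a withdrawn label for those who cannot be reached. Deaths outside the clinic can therefore be lost. Such losses would push Kaplan-Meier overall survival upward, mainly in the tdMeta cohorts.

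The direction follows from censoring people close to death. The size cannot be derived from the protocol. With an assumed true median of 12 months, the apparent median rises by about 5% (to 12.6 months) if 5% of deaths are missed and by about 39% (to 16.7 months) if 30% are missed, with censoring at last contact. The primary endpoints and cohort decisions are not affected. This is an inexpensive improvement to a secondary endpoint, worth making early because uncollected death dates may not be recoverable later.

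**What to change.** - **Sections 7.2.2.4 and 7.2.3.4:** require vital status every 3 months, recorded as date of death or date last known alive, from any available source (health record, telephone, family, public death records), whether or not a clinic visit took place.
- **Section 5.8:** keep unreachable participants in records-based survival follow-up unless they withdraw consent for it.
- **Before each overall survival analysis:** check death records, and report the number of participants with unknown vital status.

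The cost is amendment wording, possibly one line in the consent form, and a short check within the quarterly data entry that sites already do. No visit is added.
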